6. SAFETY MEASUREMENTS

6.1. Definitions

Serious adverse event (SAE) in relation to human biomedical research, means any untoward medical occurrence as a result of any human biomedical research which:

- results in or contributes to death
- is life-threatening
- requires in-patient hospitalisation or prolongation of existing hospitalisation
- results in or contributes to persistent or significant disability/incapacity or
- results in or contributes to a congenital anomaly/birth defect
- results in such other events as may be prescribed

Adverse event (AE) in relation to human biomedical research means any untoward medical occurrence as a result of any human biomedical research which is NOT serious. Adverse event can be any unfavourable and unintended sign (including an abnormal laboratory finding), symptom, or disease possibly/ probably/ definitely associated with the participant in the human biomedical research.

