1. BACKGROUND AND RATIONALE

Chronic macular diseases, such as age-related macular degeneration (AMD) and diabetic macular edema (DME) affect more than 28 million people worldwide and are currently the most common cause of irreversible vision loss and blindness in older adults in developed countries¹⁻⁵. Vision loss from macular diseases has been related to loss of independence in activities of daily living (ADLs) and a reduced quality of life (QoL)^{6,7}. For both neovascular AMD (nAMD) and DME, intravitreal injection treatment (IVT) of anti-vascular endothelial growth factor (anti-VEGF) is the gold standard treatment with excellent visual functional improvements in a large majority of patients⁸⁻¹². An intensive IVT regimen, especially in the first 2 years of the diagnosis, should be prioritized for optimal treatment outcomes¹³⁻¹⁵. However, real-world studies looking at long term IVT treatment in nAMD and DME have shown that visual outcomes compared to clinical trials are inferior, largely driven by a lower number of intravitreal injections administered¹⁶⁻¹⁸. Especially, non-adherence to long-term treatment and follow-up regimens in the management of patients with nAMD and DME in real-world ophthalmic care is common, with an estimated prevalence of 30-95%, and reduces the effectiveness of clinical treatment outcomes, conferring a higher risk for significant, permanent vision loss¹⁹⁻²³. Frequent and long-term IVT imposes a substantial burden on patients, and caregivers^{24,25}, with the most common reasons for non-adherence including patients' dissatisfaction with their vision, treatment-related anxiety, financial considerations, transport burden and access to appointments¹⁹. ***No studies to our knowledge have assessed the effectiveness of personalized patient-centred interventions to improve adherence to long term IVT treatment***^{19,22,26}.

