The proposed MPI consists of a medical consultation to optimise patients' treatment regimen, address concerns about their disease and treatment, explain advantages and disadvantages about the type of IVT medication and potential of increased treatment intervals between IVT, and address other patient and care-giver concerns.

Importantly, CAT scores will be available to the clinician to guide the consultation. Based on sub-optimal CAT scores, referral to one or a combination of services will be initiated by the study team according to a preset protocol (**Table 2**):

- (1) a referral to NE, which would include a session with a trained IVT nurse educator, who would use previously validated hard copy and digital education resources to educate the patients on their disease, symptoms, progression, and need for treatment. Factors which may cause anxiety for IVT patients such as side effects and adverse events will be addressed and the need for IVT adherence to maintain long-term vision will be reinforced. The patients would be reminded about the availability of the IVT hotline to address concerns and appointment issues.

- (2) a referral to OP who, after a needs assessment, would then carry out a comprehensive low vision assessment that includes refraction, CS, reading acuity, determination of reading goals and prescribing of suitable optical aids. OPs will assess and address any vision-related issues that may hinder reading specific tasks, navigation and other ADLs, which may be barriers to IVT adherence. They can further discuss the patient's expectations about their visual recovery and the need for IVT to maintain vision.
- (3) a referral to OT who, after a needs assessment, would provide advice about optimal lighting and, contrast perform activities of daily living retraining and functional/community mobility training, provide patient/family education and, if required, home modification to facilitate independence in ADLs, which may may allow better access to IVT appointments promoting adherence.
- (4) a referral to medical SW who, after a needs assessment, would provide the necessary emotional counselling, financial counselling and referral to community care services and other relevant support services addressing relevant barriers related to adherence to IVT.

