3. EXPECTED RISKS AND BENEFITS

There will be minimal risks involved as this intervention consist of counselling and supportive interventions to promote adherence. The participant is encouraged to raise any queries related to the questionnaires and the proposed interventions. The standard risks that apply to a standard consultation apply. There may also be other risks associated with the study that we are currently unable to foresee. Dilation of the pupil has risks involved such as potential angle closure glaucoma, however it will be performed as part of standard clinical care.

Benefits to the patient include the chance to participate in this fully funded study that aims to assess protocolised supportive interventions to promote adherence to intravitreal therapy based on sub-optimal PROMs. Improved adherence rates will lead to reduced rates of visual impairment, better disease control and ultimately contribute to better quality of life outcomes.

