7. DATA ANALYSIS

7.1. Data Quality Assurance

Participants information(data) from medical records dating up to 10 years prior and up to 24 months after informed consent is obtained will be collected. Linkage of participant identifiers to sociodemographic and questionnaire data can only be done on the request of the PI. The Investigator(s)/ Singapore National Eye Centre will permit study-related monitoring audits, MCRC and or EC review and regulatory inspection(s), providing direct access to source data/ document.

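### AEs and SAEs are recorded only when judged at least possibly caused by the research, so injection complications are not systematically captured in both randomised arms

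*Protocol*

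**What the plan says.** Protocol section 6.1 defines a non-serious event as follows: "Adverse event (AE) in relation to human biomedical research means any untoward medical occurrence as a result of any human biomedical research which is NOT" (…). The SAE definition opens in the same way: it "means any untoward medical occurrence as a result of any human biomedical research which" meets one of the listed seriousness criteria. The AE text then sets a low causal threshold, taking in any sign, "symptom, or disease possibly/ probably/ definitely associated with the participant in the human biomedical research".

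Section 6.2 calls an event related when there is a reasonable possibility that taking part caused it. It limits SAE reports to the review board (CIRB) to related ones, and asks the investigator to keep related AEs in the site file. Section 6.3 sends adverse events to the principal investigator, has the research coordinator keep one central log of every safety event, and sets a study-stopping rule on SAEs and a withdrawal rule on adverse events by grade.

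Section 5 states that the principal investigator and the treating co-investigators cannot be masked.

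On how the MPI could alter harm, Hypothesis 1 in section 2 expects more attendance and more IVT in the MPI arm. Section 1 says the MPI consultation covers the "potential of increased treatment intervals between IVT".

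**The concern.** The MPI is counselling and referral. Any ocular harm it causes or prevents would come through routine care: more injections delivered, or injections given at different intervals. These are the events that a clinician is most likely to put down to routine care rather than to the research. Under section 6.1 an event judged unrelated is not an AE or SAE at all.

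The judgement is also open to bias. The protocol does not name who decides relatedness, but it gives recording and reporting to the investigator and sends adverse events to the principal investigator, who knows the allocation. Standard-care patients receive no study intervention to which an event could readily be linked. MPI patients referred for nurse education have a session that deals with side effects, which may bring more events to notice in that arm.

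Section 1 plans for scale-up if the MPI is effective. That decision would rest on safety counts that depend on attribution, and the rules in section 6.3 would use the same counts.

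**Working it through.** The protocol states no safety rate, so there is no figure of its own to reproduce. The check is mainly a reading of the sections against each other.

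**1. What counts as an event**

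| Section | Unrelated SAE | Unrelated non-serious event |
|---|---|---|
| 6.1 | Does not exist by definition | Does not exist by definition |
| 6.2 | Implied to exist, since only the related ones are reported | No record asked for |
| 6.3 | Unclear: the log covers all safety events, but the defined events are already filtered | Unclear, for the same reason |

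The limit in 6.2 to related SAEs would be redundant if 6.1 were applied literally. The broad wording of the log in 6.3 does not settle the matter, because 6.1 supplies the only definitions. Nowhere does the protocol ask for events irrespective of attribution, and no outcome list includes injection complications.

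**2. Which harms are captured anyway**

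Section 5 collects visual acuity, contrast sensitivity and OCT-based disease-free intervals at baseline, 6, 12 and 18 months. Aim 2B compares them between arms. Vision loss is therefore measured without any attribution filter. Injection complications and other ocular events are not.

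**3. What the filter does to a comparison**

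Let *r* be the true risk per patient, *a* the share of events judged related, and *n* the patients per arm.

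Recorded count per arm = *n* × *r* × *a*. Recorded ratio, MPI to control = (*r*_MPI / *r*_control) × (*a*_MPI / *a*_control).

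The recorded ratio equals the true ratio only if the two attribution shares are equal. The documents give neither *r* nor *a*. Section 8.1 gives 160 / (1 − 0.20) = 200 patients, so *n* = 100 at 1:1. With an **assumed** true risk of 10% in both arms (10 v 10 true events), the form of the effect is:

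- *a* = 50% in both arms: 100 × 0.10 × 0.50 = 5 v 5. The ratio is right but half the events are lost.
- *a* = 50% v 10%: 5 v 100 × 0.10 × 0.10 = 1. A five-fold ratio appears where none exists.
- *a* = 0% in both arms: 0 v 0, whatever the true risks.

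The result runs from no bias to complete loss of information, depending on values the protocol does not supply. It is not an estimate.

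**4. The stopping rule**

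0.30 × 200 = 60, so the rule needs more than 60 participants with an SAE if the 200 are the denominator. Read with 6.1, only research-related SAEs count towards it. Read with the broad log in 6.3, all SAEs might.

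**5. What full capture could show**

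Power = Φ{[Δ − 1.96 √(2p̄(1 − p̄)/n)] / √[(p₁(1 − p₁) + p₂(1 − p₂))/n]}, with *n* = 100 and **assumed** risks:

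- 5% v 10%: (0.05 − 1.96 × 0.03725) / 0.03708 = −0.62, power about 27%.
- 10% v 20%: (0.10 − 1.96 × 0.05050) / 0.05 = 0.02, power about 51%.

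Even complete data would support description, not a test.

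**The case against.** The strongest reply is that little is lost. The causal threshold is low, since a possible association with taking part is enough. An event that followed an interval discussed in the MPI consultation could meet it. Section 6.2 is headed as reporting to the review board, and the log in 6.3 states no relatedness filter of its own. Record data "up to 24 months after informed consent is obtained will be collected", so the events could be recovered later. Tables by arm and extraction fields are commonly left to the SAP or case report form. The expected shift is also modest. Planned adherence rises from 60% to 80%, and 0.80 / 0.60 = 1.33; even if non-adherent patients received no injections and adherent patients equal numbers, injections would rise only 1.33-fold.

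Much of this stands as a limit on the point. It does not remove it. A low threshold is still a causal judgement by people who know the arm. Availability of records makes a remedy easy, but nothing directs anyone to extract ocular events. The defect is a stated definition, and an SAP can only tabulate what that definition lets in.

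Four stronger readings are tempting, and the document does not support them:

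- *Vision loss escapes the data.* It does not, because aim 2B compares visual acuity between arms. The statement in section 1 that poorer real-world vision is "largely driven by a lower number of intravitreal injections administered" leads into non-adherence and does not describe planned extension.
- *The arms cannot be compared on harm at all.* This holds only for recorded AE and SAE counts.
- *The control count is zero by construction.* Relatedness is to taking part, and controls also complete the questionnaires and may have added study visits and tests.
- *Section 3 shows that routine-care harms go unlogged.* It says only "Dilation of the pupil has risks involved such as potential angle closure glaucoma, however it will be performed as part of standard clinical care", which names a risk and its setting and is silent on recording.

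**Conclusion.** The point holds in a limited form. As sections 6.1 and 6.2 stand, safety events enter the trial's data only after a causal judgement made without masking. IVT complications and other ocular events of routine care are therefore not systematically captured in both randomised arms, and recorded AE and SAE counts should not be read as a fair comparison. Harm to vision is covered by the secondary outcomes.

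The three safety sections also need reconciling, including which events the stopping and withdrawal rules in 6.3 count.

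No magnitude can be given, because the documents contain no event or attribution rates. The conclusion rests on two inferences: that 6.1 governs what enters the log in 6.3, and that relatedness is judged by, or with, unmasked investigators. The intervention is supportive and the protocol describes its risk as minimal, so this is a worthwhile amendment rather than a bar to running the trial.

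**What to change.** Keep the related-only wording, but confine it to reporting to the review board. For the trial's own safety data, state that IVT complications, other ocular adverse events and all SAEs are recorded for every randomised patient irrespective of attribution, from the clinical records already used at 6, 12 and 18 months. Record relatedness as a separate judgement, and tabulate events by arm in the safety review and the final report. Reconcile 6.1, 6.2 and 6.3, and state which events the rules in 6.3 count. No threshold or clinical rule is proposed here.

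The cost is a short amendment, a few extra fields and some coordinator extraction time, with no new visits or tests. With about 100 patients per arm the comparison will be descriptive, and the report should say so. Extraction from records removes the attribution filter, but it cannot fully remove unequal detection if MPI patients have more contacts.

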6.2. Collecting, Recording and Reporting of Serious Adverse Events (SAEs) to CIRB

The reporting requirements will be in accordance to the reporting requirements published on CIRB website at the time when the event took place.

Only related SAEs (definitely/ probably/ possibly) will be reported to CIRB. Related means there is a reasonable possibility that the event may have been caused by participation in the research.

The investigator is responsible for informing CIRB after first knowledge that the case qualifies for reporting. Follow-up information will be actively sought and submitted as it becomes available.

Related AEs will not be reported to CIRB. However, the investigator is responsible to keep record of such AEs cases at the Study Site File.

6.3. Safety Monitoring Plan

The study team will conduct monthly safety reviews, with adverse events reported to the Principal Investigator within 24 hours and serious adverse events requiring immediate reporting. Participants will be withdrawn if they experience Grade 3 or higher adverse events, develop an exclusion criteria, or request withdrawal.

The study will be stopped if more than 30% of participants' experience serious adverse events, interim analysis shows no possibility of achieving study objectives, or new safety information indicates unacceptable risks.

The Principal Investigator will communicate safety concerns to all study sites via email within 48 hours of identification, with monthly safety reports distributed to all study team members. The research coordinator will maintain the central log of all safety events and ensure all site investigators receive updates.

6.4. Complaint Handling

Complaints will be handled by the research co-ordinators and if required the Quality Assurance team at the Singapore National Eye Centre.

7. DATA ANALYSIS

7.1. Data Quality Assurance

Participants information(data) from medical records dating up to 10 years prior and up to 24 months after informed consent is obtained will be collected. Linkage of participant identifiers to sociodemographic and questionnaire data can only be done on the request of the PI. The Investigator(s)/ Singapore National Eye Centre will permit study-related monitoring audits, MCRC and or EC review and regulatory inspection(s), providing direct access to source data/ document.

7.2. Data Entry and Storage

Research data and participant databases will be stored in a secured SERI PHR shared drive. As for the hard copies, they will be stored in the SERI Academia office at Level 6, in a locked cabinet. The principal investigator (PI), co-investigators (Co-I) and CRCs will have access to these data, and this access can be monitored through computer records. Questionnaire data will be entered through an internet-enabled tablet and stored on an IHiS approved secure cloud server hosted in Singapore via AWS as described previously.

8. SAMPLE SIZE AND STATISTICAL METHODS

8.1. Determination of Sample Size

Specific Aim 1 and 2: The primary outcome comparison of adherence rates to IVT treatment between the MPI arm versus standard care at various follow-up time points with 18 months as the main time point. It is estimated that the baseline non-adherence rate with standard care arm is 40% (SD=2). Considering a reduction of the non-adherence rate to 20% as a clinically significant difference, and assuming a power of 80% and a two-sided level of significance at 5%, the minimum sample size

required is 79 patients per arm (rounded up to 160 patients in total). Assuming a maximum 20% dropout in the study we estimate a sample size of 200 patients (Specific aim 1).

For secondary outcomes such as the improvement of QoL as assessed by the various CAT domain scores, we assume a modest effect size difference of 0.5 between the two arms. Using a power of 80%, a two-sided level of significance at 5%, and the maximum 20% dropout rate, we estimate the required sample size is 158 (79 per arm) (Specific aim 2A). Hence, this is included in the larger sample size calculated above.

Specific aim 3: There is no *a priori* sample size required for qualitative interviews. We will continue our semi-structured interviews until thematic saturation is reached (i.e. no new themes emerge). Based on previous studies by our group^{31,67}, we anticipate the need to interview between 5-10 participants for each stakeholder group to obtain data saturation, broadly: (a) clinicians using CATs and MPI, (b) NE, OP, OT and SW involved in administering MPI (c) patients involved in this study, and (d) caregivers of patients. For the purposes of estimating a budget for this grant proposal, we state an indicative sample size of 40 interview participants i.e. 10 in total for stakeholder group a and b, and 30 for stakeholder group c and d (patients and caregivers).

Specific aim 4: The sample size required for cost-effectiveness analysis is usually larger than clinical studies as it involves estimating the joint distribution of patient outcomes and costs. Furthermore, power calculations require setting a willingness-to-pay threshold, which is not known for Singapore. However, as cost-effectiveness is more concerned with estimating effect size rather than hypothesis testing, it can still provide valuable information even if underpowered. Instead of confidence intervals, sensitivity analysis will be used to assess the range of estimated values.

8.2. Statistical and Analytical Plans

Specific aim 1: Planned statistical analysis for the primary outcome measure will be the difference in percentage of adherence rate between the standard care and MPI arm assessed by the chi-square test or Fisher's exact test. Cox proportional hazards model will be used to assess the independent effect of MPI on adherence rates, after adjusting for age, baseline CAT scores, visual function, anatomical outcomes, type of IVT medication given, and disease-free intervals.

Specific aims 2A and 2B: CAT scores will be assessed with a two-sample t-test to compare the differences in mean CAT scores between the 2 arms. Linear mixed models will be used to assess the independent effect of MPI on follow-up CAT scores, after adjusting for fixed effects terms such as age, baseline CAT scores, visual function, anatomical outcomes, type of IVT medication given, and disease-free intervals, and a random slope term follow-up time (measured in months).

Specific aim 3 Interviews will be conducted in-person or online, audio-recorded, and transcribed verbatim by professional transcribers (i.e. transcriptions outsourced to third party). Designated researchers in the study team will check a random 10% sample of interview transcriptions for accuracy, prior to qualitative data analysis. If errors or inaccuracies are found in the random sample of transcripts, then 100% of the transcripts will need to be checked and edited for accuracy, prior to data analysis. We will analyse the qualitative data as per Gale et al's thematic analysis⁶². NVivo software will be used to manage qualitative data analysis. A standardised questionnaire to assess implementation outcomes will also be administered to all the stakeholders for a quantitative assessment.

Specific aim 4: To assess the cost-effectiveness analysis of the MPI, we will develop a cohort-based Markov model embedded within a decision tree to simulate the net lifetime cost and effectiveness of the MPI compared to standard care. The model's health states will be defined by VA ranges, consistent with prior cost-effectiveness studies for of macular disease treatments^{63,64}. We will quantify the incremental costs of implementing the MPI using an activity-based costing approach, which includes all non-sunk costs – such as labour, materials and supplies, and amortized technology and rental costs – associated with treating each patient. These costs will be categorized by key activities, including physician/nurse/allied health training, CAT assessment, and referral to personalized programs. Treatment costs will be based on non-subsidized bill sizes, which are expected to approximate actual costs. Data on health resource utilization and costs incurred during the first 18 months will come from this study. For benefits, which are measured in terms of QALYs gained, QoL weights will be measured for month 18 using the EQ-5D instrument and validated local preference weights⁶⁵. The key difference between the MPI and standard care will be the proportion of IVT-adherent patients, influencing costs and long-term VA outcomes. As these differences likely persist over a patient's remaining lifetime, the model will extrapolate long-term VA and corresponding quality-of-life weights based on published trajectories for treated (adherent) and untreated (non-adherent) patients⁶⁶. With each subsequent annual cycle, the surviving cohort will accrue costs and QALYs associated with their VA and IVT adherence status. This model will be used to estimate the incremental cost-effectiveness ratio (ICER) for the MPI. We will also conduct one-way and n-way sensitivity analyses for all key model inputs and present cost-effectiveness acceptability curves showing the probability that the MPI is cost-effective at various willingness-to-pay thresholds policymakers may consider. We will also conduct scenario analyses to investigate the robustness of our results to alternative assumptions on long-run VA trajectories.

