4.3. Inclusion Criteria

Inclusion criteria will include patients with chronic macula disease including those diagnosed with nAMD and DME, who require IVT. This would include treatment naïve patients (no IVT in either eye the last 6 months) and previously treated patients who have had IVT in either eye in the last 6 months and require further IVT treatment at the baseline study visit in either eye. All participants will be able to provide

informed consent, speak English or Mandarin, be a Singapore resident and must consent to undergoing the MPI intervention.

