- Following baseline assessment, **participants with suboptimal CAT scores (Cohort 1-<50 in any domain)** will be included in the RCT and randomly allocated in a 1:1 ratio to either the intervention group (personalised multi-disciplinary protocolised intervention, MPI) or the control group (standard care). Randomisation will be conducted using a computer-generated random sequence created by an independent biostatistician not involved in recruitment or outcome assessment. To ensure balance across disease types, randomisation will be stratified by diagnosis (neovascular age-related macular degeneration [nAMD] vs. diabetic macular edema [DME]). Allocation concealment will be maintained using sequentially numbered, opaque, sealed envelopes prepared by an independent study coordinator. The envelopes will only be opened after baseline data collection to assign participants to their respective groups. Co-Is that are not treating clinicians and data analysts will remain blinded to group allocation, although masking of participants and principal investigator and Co-Is who are the treating clinicians will not be feasible due to the nature of the intervention.

- For the MPI arm, the CAT scores integrated into the electronic medical records will be used to formulate **an automated protocolized standardized MPI for all patients based on the domain specific scores that are sub-optimal** (See **Table 2**). All MPI patients will receive *a medical consultation (compulsory) and an addition of Intervention 1-4 (electives, 1) NE, 2) OP, 3) OT, 4) SW*. In the MPI arm, these referrals would be automatically triggered by the study team based on baseline CAT scores and the treating clinician will be informed. The MPI visits will take place on the same day as standard clinical visits where possible, however additional MPI study visits may be needed if there are scheduling challenges. Referral adherence to the MPI appointments and intervention will be assessed.

Sub-optimal scores are defined as any domain where the scores are below 50 at baseline or have reduced by 25% from the baseline visit. Table 2 summarizes the MPI interventions that are relevant to each CAT domain. A tailored MPI will be formulated and recommended to the patient at baseline, or at a follow-up time-points where domain scores decrease, and the MPI should be completed within 4 months.

Table 2: Standardised personalised MPI based on sub-optimal CAT domain-specific scores

| Ret CAT | | MacCAT | |

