At each follow up time point, based on the previous scheduled follow-up appointments and recommended IVT schedule, the study team will assess if the patient has been “adherent” or “non-adherent”. If the patient does not visit the clinic within the range of the follow-up time points or does not attend the scheduled study visit, phone calls will be made to determine reasons or barriers for adherence. A remote invitation to complete the CAT questionnaire will also be sent to these patients or if uncontactable, they will be approached and interviewed at their next clinical visit. For previously treated patients, previous adherence status up to 2 years prior to study enrolment for the time of IVT treatment will be recorded by the study team from medical records.

Secondary outcome measures will be assessed at baseline and 6, 12, and 18 month follow up visits (+/- 8 weeks) including:

- CAT scores (Specific aim 2A) from the CAT questionnaire database
- Visual function -Monocular and binocular presenting corrected VA and CS (Specific aim 2B) will be collected from the clinical records. If data are not present, the CRCs will conduct these tests on participants using standardized protocols.
- Disease free intervals as defined by the maximum IVT treatment interval where no disease activity recurrence is detected on OCT will be collected from clinical records and OCT images from the clinical database (Specific aim 2B)
- Tertiary outcome measures include the acceptability, adoptability, appropriateness, feasibility, fidelity through mixed method testing with interviews and questionnaires (Specific aim 3).
- The costs of MPI, baseline and 18-month assessment of Euro-quality of life (EQ-5D) to assess QALYs (Specific aim 4)

Qualitative and quantitative analysis of key stakeholders (Specific aim 3)

The PI, assisted by their Co-Is and collaborators, will identify eligible individuals for qualitative interviewing that will be performed with major stakeholders between 6 to 15 months timeline. These include the clinicians, nurses and the allied health specialists (OP, OT and SW) who will be involved in administering the MPI, and patients and care-givers who receive the MPI. Potential individuals will be contacted over email or phone call, and a trained study team will follow up on affirmative responses by obtaining written informed consent to carry out the following study procedures:

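### The primary adherence test ignores the randomisation stratum and recorded prior adherence, and the only adjusted adherence model does not estimate the powered 18-month difference; the cost is modest and the test stays valid.

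*Protocol*

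**What the plan says.** For Specific aim 1, section 8.2 makes the primary analysis the "difference in percentage of adherence rate between the standard care and MPI arm assessed by the chi-square test", with Fisher's exact test named as an alternative. It then says that a "Cox proportional hazards model will be used to assess the independent effect of MPI on adherence rates". The covariates for that model are given as a closed list: "after adjusting for age, baseline CAT scores, visual function, anatomical outcomes, type of IVT medication given, and disease-free intervals". Diagnosis and prior adherence are not on that list. The linear mixed model in the same section is for CAT scores, not adherence.

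Section 5 says that "randomisation will be stratified by diagnosis" and that patients are "randomly allocated in a 1:1 ratio". Under the study schedule in section 5, for previously treated patients, "previous adherence status up to 2 years prior to study enrolment for the time of IVT treatment will be recorded". Section 4.3 also admits treatment-naive patients, described as having had "no IVT in either eye the last 6 months".

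The endpoint in section 5 is a yes/no adherence status judged at 6, 12 and 18 months. Section 8.1 makes 18 months the main time point and sizes the trial on non-adherence falling from 40% to 20%, with 80% power at a two-sided 5% level. That gives 79 per arm, 160 in total, and 200 after 20% dropout.

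**The concern.** There are three mismatches between the design and the stated analysis.

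- **Stratum.** Randomisation is balanced on diagnosis, but the analysis does not use it. If diagnosis predicts adherence, the unstratified test uses a slightly too large variance and becomes conservative.
- **Prior adherence.** Past adherence is a plausible predictor of future adherence. The team will collect it for part of the sample, but no stated analysis uses it.
- **Effect measure.** The powered quantity is a difference in proportions at 18 months. The only adjusted adherence analysis gives a hazard ratio, and the protocol defines no event, time origin or censoring rule for it. The adjusted result would therefore not be an adjusted version of the primary result.

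The primary test is also left as one of two tests with different power at the planned size. At stake are some precision and a single, clear primary result. The validity of the trial is not in question.

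**Working it through.** **Inputs.** From section 8.1: non-adherence 40% (control) and 20% (MPI), power 80%, two-sided 5%, 20% dropout. From section 5: 1:1 allocation and two diagnosis strata. The protocol does not say how strongly diagnosis or prior adherence predicts the outcome, so those values are assumptions.

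**1. The stated size.** With unpooled variance, n per arm = (1.960 + 0.842)² × (0.4×0.6 + 0.2×0.8) / 0.2² = 78.49, so 79. This matches. Also 160 / 0.8 = 200, which matches.

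**2. Exact power of the two named tests** (enumeration over both binomials, 40% versus 20%):

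| Per arm | Chi-square, uncorrected | Fisher's exact |
|---|---|---|
| 79 | 79.5% | 73.8% |
| 80 | 80.1% | 74.5% |

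Fisher's exact test needs about 90 per arm for 80% power (80.2% at 90).

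**3. Expected cells at 80 per arm.** Non-adherent patients: 80×0.4 + 80×0.2 = 32 + 16 = 48. The expected count is therefore 48 / 2 = 24 non-adherent and 80 − 24 = 56 adherent in each arm. Small cells give no reason to use Fisher's test.

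**4. What the hazard ratio implies.** Suppose the event is first non-adherence and hazards are proportional. Then 40% versus 20% at 18 months gives HR = ln(0.8) / ln(0.6) = 0.437. With control risk p, the MPI risk is 1 − (1 − p)^0.437:

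| Control non-adherence | MPI non-adherence | Difference (points) |
|---|---|---|
| 30% | 14.4% | 15.6 |
| 40% | 20.0% | 20.0 |
| 50% | 26.1% | 23.9 |
| 60% | 33.0% | 27.0 |

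One hazard ratio fits differences from 15.6 to 27.0 points, so on its own it does not give the powered quantity. Power on the Cox scale is not the difficulty: 48 expected events give about 82%, and 46 are needed.

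**5. Value of the two variables.** This was simulated with 4,000 trials per setting at 80 per arm. Assumptions: diagnosis split 50:50; 40% naive, 36% previously adherent, 24% previously non-adherent; odds ratio 1 to 3 for diagnosis and 1 to 6 for prior non-adherence.

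| Analysis | Power | Rejection rate under no effect |
|---|---|---|
| Chi-square | 0.79–0.81 | 0.036–0.052 |
| CMH by diagnosis | 0.79–0.82 | 0.040–0.055 |
| Logistic, with diagnosis and prior status | 0.79–0.85 | 0.041–0.059 |
| Standardised risk difference from that model | 0.80–0.86 | 0.045–0.063 |

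The simulation standard error is about √(0.8×0.2/4000) = 0.006 for power and √(0.05×0.95/4000) = 0.003 for the rejection rate.

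Other settings widen the range. If every patient had a prior-adherence status, 40% were non-adherent and the log odds ratio were 1.5 to 2.0 (odds ratio 4.5 to 7.4), power reaches about 84–87%. If prior adherence does not predict the outcome, the finer strata cost about 1 point. Over all settings, diagnosis alone adds about 0 to 1.5 points, and prior adherence changes power by about -1 to +7.

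**The case against.** The strongest reply is that nothing here is broken. The unadjusted chi-square is valid, matches the basis of the sample size and has the stated power. Its error rate under no effect stays near 4–5%. Stratifying by diagnosis barely moves the power, and the larger gains need a strong predictor that the protocol does not document and that treatment-naive patients cannot have. All of this stands, and it limits the weight of the point.

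Two further replies stand in part. Naming chi-square or Fisher's test is common shorthand for using Fisher's only when expected cells are small. On that convention chi-square would be used, and the 74.5% would not apply. But the protocol gives no selection rule, and the design rates leave no need for the alternative. Also, the Cox model is supplementary. Because adherence requires every appointment to be kept within its window, time to first failure is a coherent reading, and it can use follow-up before dropout. That justifies keeping it as support. It does not justify having it as the only adjusted analysis of a binary 18-month endpoint.

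A statistical analysis plan, not shown here, may add detail. The protocol nevertheless already names the tests and the covariates.

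A reader might also infer that patients counted as naive after 6 months without an injection are lapsed, and so the clearest prior non-adherers. The documents do not support that. Section 5 judges adherence against what the doctor recommended, so a patient for whom no injection was recommended in that period was not non-adherent.

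**Conclusion.** The point holds as a matter of efficiency and alignment. The stated adherence analyses use neither the randomisation stratum nor a predictor that the team will record, and the one adjusted model reports a different effect measure from the one powered. The Fisher shortfall (74.5% against 80.1% at 80 per arm) follows from the protocol's own rates, but matters only if that test is used. The mismatch of effect measures needs no assumption about predictors; the 15.6 to 27.0 point illustration assumes a first-failure event and proportional hazards. The gains of about 0 to 1.5 points (diagnosis) and -1 to +7 points (prior adherence) rest on assumed prognostic strengths.

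It would be tempting to conclude that the primary test is invalid or the trial underpowered. Neither follows: the chi-square controls its error rate, and the size of 79 per arm reproduces.

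**What to change.** In section 8.2, for Specific aim 1:

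- Make the primary test Cochran-Mantel-Haenszel stratified by diagnosis, at 18 months, and report the stratified risk difference with its 95% CI.
- Remove Fisher's exact test as an alternative.
- Make the main adjusted analysis a logistic regression for 18-month adherence, reported as a standardised risk difference. Its terms are arm, diagnosis, age, baseline CAT and a three-level prior status: no recorded prior treatment, previously adherent, previously non-adherent, as section 5 already has it recorded.
- Do not class patients without an injection for 6 months as non-adherent by default.
- Keep any Cox model as supportive only, with its event, time origin and censoring defined.

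Fix this before outcome data are seen. The sample size does not change. The cost is a revised paragraph and a few more model terms, with no gain, and possibly about a point of power lost, if prior adherence predicts little.
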